4.10.2. Modifications to the Approved Statistical Analysis Plan

Section (SAP v1.0)	Update (SAP Amendment v2.0)
Section 4.1 General considerations.	
 ○ To update the imputation rule for viral parameters by removing “LOD” and imputing TND as 0. ○ To add the definitions of EOT, EOT assessment and EOT+24 weeks assessment. ○ To add the efficacy endpoint summary for participants who qualified to discontinue the TDF/TD.
Section 4.2.1 Participant disposition	To add the number of participants who signed the informed consent form, and the number of participants screened.
Section 4.2.5 Protocol deviations	To remove the summary of the PD table.
Section 4.3 Primary endpoint analysis	To update the sensitivity analysis.
Sections 4.4.1 and 4.5.1 Secondary and exploratory endpoints analysis	
 ○ To update the timepoints due to study early termination, and add additional analysis for sustained suppression of HBV DNA, and sustained suppression of HBV DNA with HBsAg loss. ○ To update the analysis of “time to xx”. ○ To update HBeAg and anti-HBe timepoints for the summary. ○ To update the virological relapse summary. ○ To add the plots for ALT and HBV DNA.
Sections 4.5.3 and 4.8.2 Exploratory endpoints for immunogenicity and immunogenicity analysis	
 ○ To exclude the analysis of ADA to VIR-2218. ○ To remove the analysis visit (with analysis window) for the ADA data.
Section 4.7.1 Extend of exposure	To update the analysis of exposure.
Section 4.7.3 Adverse event	
 ○ To move the local tolerability of VIR-3434 from Section 4.7.6 to Section 4.7.3. ○ To add the table of study intervention related TEAEs.
Section 4.8.1 Pharmacokinetics analysis	To remove the PK listing for the PK sampling time deviation.

Sections 4.9 and 4.10.1 Interim analysis and modifications to the approved study protocol	To update the changes of the interim analyses.
Appendix 2. Analysis windows for study assessment	To update the EOT date for the analysis window and address the typo in the analysis window for the Follow-up tables 11, 12 and 13.
Others: words/sentences, format, etc.	Other minor edits, updates, etc.

5. SAMPLE SIZE DETERMINATION

Sample size calculation for the initial assessment of an investigational regimen is based on HBsAg loss rate as described below ([FDA 2018](#); [Terrault 2018](#)).

- An investigational regimen will initially be evaluated in an open-label single-arm study, without a concurrent control arm. If the true HBsAg loss rate ranges from 25% to 40%, at least 10 participants will be required to provide > 70% statistical power to detect a 23% difference in HBsAg loss rate, using a 1-sided exact binomial test with a significance level of 0.025 ([Table 6](#)).

Table 6: Power and Sample Size Calculation for Single-Arm Efficacy

Null Hypothesis: Response rate is $\leq 2\%$, which is the assumed rate in NRTI-suppressed participants. Assumptions: Use exact binomial test with 1-sided significance level of 0.025.		
Sample Size	Power to detect a 23% difference in HBsAg loss rate, if the true HBsAg loss rate is 25%	Power to detect a 38% difference in HBsAg rate, if the true HBsAg loss rate is 40%
10	75.6%	95.4%
15	76.4%	97.3%
25	96.8%	> 99%
30	98.9%	> 99%

This study is exploratory in nature, and there is no hypothesis testing. The sample size of the study is estimated, referring to the calculation above and based on practical considerations. A sample size of 10 or 15 will be initially enrolled in each cohort.

Up to 60 participants will be enrolled in this sub-study initially. Additionally, up to 30 floater participants may be added to the cohorts. As described in Section 9.5 of the Protocol, this addition may be based on data from an interim analysis. No more than 90 participants will be enrolled.

6. SUPPORTING DOCUMENTATION

APPENDIX 1. LIST OF ABBREVIATIONS AND DEFINITIONS OF TERMS

AASLD	American Association for the Study of Liver Diseases
ADA	anti-drug antibodies
AE	adverse event
ALT	alanine transaminase
Anti-HBe	hepatitis B e antibody
Anti-HBs	hepatitis B surface antibody
AST	aspartate transaminase
BMI	body mass index (kg/m ²)
BQL	below limit of quantification
CI	confidence interval
CLDQ-HBV	Chronic Liver Disease Questionnaire-Hepatitis B
CM	concomitant medication
CRO	contract research organization
CTCAE	Common Terminology Criteria for Adverse Events
DNA	deoxyribonucleic acid
EASL	The European Association for the Study of the Liver
ECG	electrocardiogram
eCRF	electronic case report form
ECI	Events of Clinical Interest
EOS	End of Study
HBcrAg	hepatitis B core-related antigen
HBV	hepatitis B virus
HBeAg	hepatitis B e antigen
HBsAg	hepatitis B surface antigen
INR	international normalized ratio
LLN	lower limit of normal
LLOQ	lower limit of quantitation
Max	maximum value
MedDRA	Medical Dictionary for Regulatory Activities
Min	minimum value

PDs	protocol deviations
PK	pharmacokinetic/pharmacokinetics
PT	preferred term
Q1	first quartile
Q3	third quartile
RNA	ribonucleic acid
SAE	serious adverse event
SAP	statistical analysis plan
SC	subcutaneous
SD	standard deviation
SOC	system organ class
T(N)D	target (not) detected
TE	treatment-emergent
TEAE	treatment-emergent adverse event
TFLs	tables, figures, and listings
ULN	upper limit of normal
WHODD	World Health Organization Drug Dictionary

CCI

APPENDIX 2. ANALYSIS WINDOWS FOR STUDY ASSESSMENT

Notes:

- The analysis windows will be applied using the following rules for both scheduled and unscheduled visits:
 - a. If no numerical measurement is available within an analysis window, the measurement will be considered missing for the visit.
 - b. If there is more than 1 numerical measurement available within an analysis window, use the following rules:
 - i. The scheduled visit measurement will be used if it is available;
 - ii. The unscheduled visit measurement closest to the target day will be used unless the scheduled visit is available; or
 - iii. If there are multiple unscheduled visit measurements at the same distance from the target day, the latest measurement will be used.
- For the study assessments, e.g., laboratory, ECG, and vital sign measurements, collected on the date of the first dose of study drug, the following rules will be applied if it cannot be determined whether the measurement is before or after the first dose:
 - a. Scheduled measurement will be treated as a pre-dose observation.
 - b. Unscheduled measurement will be treated as a post-dose observation.
- Analysis Visits: The visit name for analysis purpose is used to report data in tables and figures.
- The Analysis Window is continuous, without leaving any date gaps between visits (no gap date). The Analysis Window boundaries are left exclusive, right inclusive, except specified otherwise.

Table 7: Analysis Windows for Safety, Efficacy, and other Assessments: Treatment Period for Cohort 1a/2a

Study Stage	Screening	Treatment Period												
Visit Week		W1	W4	W8	W12	W16	W20	W24	W28	W32	W36	W40	W44/ EOT	
Visit Day ± Visit Window	D -56 to -1	D1	D8±2	D29±2	D57±2	D85±2	D113±2	D141±2	D169±2	D197±2	D225±2	D253±2	D281±2	D309±2
Analysis Visit	Week 1 Day 1 (Baseline)	Week 1 Day 8	Week 4	Week 8	Week 12	Week 16	Week 20	Week 24	Week 28	Week 32	Week 36	Week 40	Week 44 /EOT	
Analysis Window	< D1 dose time	≥D1 dose time, +7	±14	±14	±14	±14	±14	±14	±14	±14	±14	±14	-14, EOT Date	
HBsAg quantitative, HBV DNA quantification, Liver function tests, Serum chemistry, Hematology, Coagulation parameters.														
Analysis Visit	Week 1 Day 1 (Baseline)		Week 4	Week 8	Week 12	Week 16	Week 20	Week 24	Week 28	Week 32	Week 36	Week 40	Week 44 /EOT	
Analysis Window	< D1 dose time		≥D1 dose time, +14	±14	±14	±14	±14	±14	±14	±14	±14	±14	-14, EOT Date	
Anti-HBs quantitative, HBeAg quantitative, HBcrAg, HBV RNA.														
Analysis Visit	Week 1 Day 1 (Baseline)		Week 4		Week 12		Week 20			Week 32			Week 44 /EOT	
Analysis Window	< D1 dose time		≥D1 dose time, +28		±28		-28, +42			±42			-42, EOT DATE	
CLDQ-HBV, WPAI:GH.														

Table 8: Analysis Windows for Safety, Efficacy, and other Assessments: Treatment Period for Cohort 3a

Study Stage	Screening	Treatment Period											
Visit Week		W1	W4	W8	W12	W16	W20	W24	W28	W32	W36/ EOT ^a	W40/ EOT ^a	
Visit Day ± Visit Window	D -56 to -1	D1	D8±2	D29±2	D57±2	D85±2	D113±2	D141±2	D169±2	D197±2	D225±2	D253±2	D281±2
Analysis Visit	Week 1 Day 1 (Baseline)	Week 1 Day 8	Week 4	Week 8	Week 12	Week 16	Week 20	Week 24	Week 28	Week 32	Week 36 /EOT ^b	Week 40 /EOT ^c	
Analysis Window	< D1 dose time	≥D1 dose time, D8+7	±14	±14	±14	±14	±14	±14	±14	±14	±14	-14, EOT DATE	
HBV DNA quantification, HBsAg quantitative, Liver function tests, Serum chemistry, Hematology, Coagulation parameters.													
Analysis Visit	Week 1 Day 1 (Baseline)		Week 4	Week 8	Week 12	Week 16	Week 20	Week 24	Week 28	Week 32	Week 36 /EOT ^b	Week 40 /EOT ^c	
Analysis Window	< D1 dose time		≥D1 dose time, +14	±14	±14	±14	±14	±14	±14	±14	±14	-14, EOT DATE	
Anti-HBs quantitative, HBeAg quantitative, HBcrAg, HBV RNA.													
Analysis Visit	Week 1 Day 1 (Baseline)		Week 4		Week 12		Week 20			Week 32	Week 36 /EOT ^b	Week 40 /EOT ^c	
Analysis Window	< D1 dose time		≥D1 dose time, +28		±28		-28, +42			-42, +14	±14	-14, EOT DATE	
CLDQ-HBV, WPAI:GH.													

^a If Q8W dosing regimen is chosen, then W40 will be the EOT visit and assessments for EOT should be done at W40. Similarly, if Q12W dosing regimen is chosen then W36 will be the EOT and assessments for EOT should be done at W36.

^b To be conducted if W36 will be EOT (Q12W dosing regimen).

^c To be conducted if W40 will be EOT (Q8W dosing regimen).

Table 9: Analysis Windows for Safety, Efficacy, and other Assessments: Treatment Period for Cohort 4a

Study Stage	Screening	Treatment Period													
		W1		W4	W8	W12	W16	W20	W24	W28	W32	W36	W40	W44/ EOT	
Visit Week															
Visit Day ± Visit Window	D -56 to -1	D1	D2	D8 ±2	D29 ±2	D57 ±2	D85 ±2	D113 ±2	D141 ±2	D169 ±2	D197 ±2	D225 ±2	D253 ±2	D281 ±2	D309 ±2
Analysis Visit	Week 1 Day 1 (Baseline)	Week 1 Day 2	Week 1 Day 8	Week 4	Week 8	Week 12	Week 16	Week 20	Week 24	Week 28	Week 32	Week 36	Week 40	Week 44 /EOT	
Analysis Window	< D1 dose time	≥D1 dose time, +2	-4, +7	±14	±14	±14	±14	±14	±14	±14	±14	±14	±14	-14, EOT DATE	
HBV DNA quantification, HBsAg quantitative, Liver function tests, Serum chemistry, Hematology, Coagulation parameters.															
Analysis Visit	Week 1 Day 1 (Baseline)	Week 1 Day 2		Week 4	Week 8	Week 12	Week 16	Week 20	Week 24	Week 28	Week 32	Week 36	Week 40	Week 44 /EOT	
Analysis Window	< D1 dose time	≥D1 dose time, +13		±14	±14	±14	±14	±14	±14	±14	±14	±14	±14	-14, EOT DATE	
Anti-HBs quantitative, HBeAg quantitative.															
Analysis Visit	Week 1 Day 1 (Baseline)			Week 4	Week 8	Week 12	Week 16	Week 20	Week 24	Week 28	Week 32	Week 36	Week 40	Week 44 /EOT	
Analysis Window	< D1 dose time			≥D1 dose time, +14	±14	±14	±14	±14	±14	±14	±14	±14	±14	-14, EOT DATE	
HBcrAg, HBV RNA.															
Analysis Visit	Week 1 Day 1 (Baseline)			Week 4		Week 12		Week 20			Week 32			Week 44 /EOT	
Analysis Window	< D1 dose time			≥D1 dose time, +28		±28		-28, +42			±42			-42, EOT DATE	
CLDQ-HBV, WPAI:GH.															

Table 10: Analysis Windows for Safety, Efficacy, and other Assessments: Treatment Period for Cohort 5a

Study Stage	Screening	Treatment Period															
		W1				W4	W8	W12	W16	W20	W24	W28	W32	W36	W40	W44	W48/EOT
Visit Week																	
Visit Day ± Visit Window	D -56 to -1	D1	D2	D8 ±2	D29 ±2	D57 ±2	D85 ±2	D113 ±2	D141 ±2	D169 ±2	D197 ±2	D225 ±2	D253 ±2	D281 ±2	D309 ±2	D337 ±2	
Analysis Visit	Week 1 Day 1 (Baseline)		Week 1 Day 2	Week 1 Day 8	Week 4	Week 8	Week 12	Week 16	Week 20	Week 24	Week 28	Week 32	Week 36	Week 40	Week 44	Week 48/EOT	
Analysis Window	< D1 dose time	≥D1 dose time, +2	-4, +7	±14	±14	±14	±14	±14	±14	±14	±14	±14	±14	±14	±14	-14, EOT DATE	
HBV DNA quantification, HBsAg quantitative, Liver function tests, Serum chemistry, Hematology, Coagulation parameters																	
Analysis Visit	Week 1 Day 1 (Baseline)		Week 1 Day 2		Week 4	Week 8	Week 12	Week 16	Week 20	Week 24	Week 28	Week 32	Week 36	Week 40	Week 44	Week 48/EOT	
Analysis Window	< D1 dose time	≥D1 dose time, +13		±14	±14	±14	±14	±14	±14	±14	±14	±14	±14	±14	±14	-14, EOT DATE	
Anti-HBs quantitative, HBeAg quantitative																	
Analysis Visit	Week 1 Day 1 (Baseline)		Week 1 Day 2		Week 4	Week 8	Week 12	Week 16	Week 20	Week 24	Week 28	Week 32	Week 36	Week 40	Week 44	Week 48/EOT	
Analysis Window	< D1 dose time	≥D1 dose time, +13		±14	±14	±14	±14	±14	±14	±14	±14	±14	±14	±14	±14	-14, EOT DATE	
HBcrAg, HBV RNA																	
Analysis Visit	Week 1 Day 1 (Baseline)			Week 4		Week 12		Week 20			Week 32			Week 44		Week 48/EOT	
Analysis Window	< D1 dose time			≥D1 dose time, +28		±28		-28, +42			±42			-42, +14		-14, EOT Date	
CLDQ-HBV, WPAI:GH																	

Table 11: Analysis Windows for Safety, Efficacy, and other Assessments: Follow-Up Period for Participants Who Never Discontinue NRTI during Follow-Up Period

Study Stage	Follow-Up Period								
	Follow up Visit	F1	F4	F8	F12	F16	F20	F24	F36
Visit Day ± Visit Window	D8 ±2	D29 ±7	D57 ±7	D85 ±7	D113 ±7	D141 ±7	D169 ±7	D253 ±7	D337 ±7
Analysis Visit	FU Week 1	FU Week 4	FU Week 8	FU Week 12	FU Week 16	FU Week 20	FU Week 24	FU Week 36	FU Week 48/EOFU
Analysis Window	EOT DATE , +7	±14	±14	±14	±14	±14	-14, +42	±42	-42, +14
HBV DNA quantification, HBsAg quantitative, Liver function tests, Serum chemistry, Hematology, Coagulation parameters, Anti-HBs quantitative, HBeAg quantitative, Anti-HBe qualitative.									
Analysis Visit	FU Week 1	FU Week 4		FU Week 12			FU Week 24		FU Week 48/EOFU
Analysis Window	EOT DATE , +7	-14, +28		-28, +42			-42, +84		-84, +14
HBcrAg, HBV RNA.									
Analysis Visit	FU Week 1			FU Week 12			FU Week 24		FU Week 48/EOFU
Analysis Window	EOT DATE , +35			±42			-42, +84		-84, +14
CLDQ-HBV, WPAI:GH.									

Table 12: Analysis Windows for Safety, Efficacy, and other Assessments: Follow-Up Period for Participants Who Discontinue NRTI at F1

Study Stage	Follow-Up Period															
	Follow up Visit	F1	F2	F4	F6	F8	F10	F12	F16	F20	F24	F28	F32	F36	F40	F44

Visit Day ± Visit Window	D8 ±2	D15 ±2	D29 ±7	D43 ±7	D57 ±7	D71 ±7	D85 ±7	D113 ±7	D141 ±7	D169 ±7	D197 ±7	D225 ±7	D253 ±7	D281 ±7	D309 ±7	D337 ±7
Analysis Visit	FU Week 1	FU Week 2	FU Week 4	FU Week 6	FU Week 8	FU Week 10	FU Week 12	FU Week 16	FU Week 20	FU Week 24	FU Week 28	FU Week 32	FU Week 36	FU Week 40	FU Week 44	FU Week 48/EOFU
Analysis Window	EOT DATE ,+2	-5, +7	±7	±7	±7	±7	-7, +14	±14	±14	±14	±14	±14	±14	±14	±14	±14
HBV DNA quantification, HBsAg quantitative, Liver function tests, Serum chemistry, Hematology, Coagulation parameters, Anti-HBs quantitative, HBeAg quantitative, Anti-HBe qualitative.																
Analysis Visit	FU Week 1		FU Week 4				FU Week 12			FU Week 24						FU Week 48/EOFU
Analysis Window	EOT DATE ,+7		-14, +28				-28, +42			-42, +84						-84, +14
HBcrAg, HBV RNA.																
Analysis Visit	FU Week 1						FU Week 12			FU Week 24						FU Week 48/EOFU
Analysis Window	EOT DATE ,+35						±42			-42, +84						-84, +14
CLDQ-HBV, WPAI:GH.																

Table 13: Analysis Windows for Safety, Efficacy, and other Assessments: Follow-Up Period for Participants Who Discontinue NRTI at F12

Study Stage	Follow-Up Period															
Follow up Visit	F1	F4	F8	F12	F14	F16	F18	F20	F22	F24	F28	F32	F36	F40	F44	F48/EOFU
Visit Day ± Visit Window	D8 ±2	D29 ±7	D57 ±7	D85 ±7	D99 ±7	D113 ±7	D127 ±7	D141 ±7	D155 ±7	D169 ±7	D197 ±7	D225 ±7	D253 ±7	D281 ±7	D309 ±7	D337 ±7
Analysis Visit	FU Week 1	FU Week 4	FU Week 8	FU Week 12	FU Week 14	FU Week 16	FU Week 18	FU Week 20	FU Week 22	FU Week 24	FU Week 28	FU Week 32	FU Week 36	FU Week 40	FU Week 44	FU Week 48/EOFU
Analysis Window	EOT DATE ,+7	±14	±14	-14, +7	±7	±7	±7	±7	±7	-7, +14	±14	±14	±14	±14	±14	±14

HBV DNA quantification, HBsAg quantitative, Liver function tests, Serum chemistry, Hematology, Coagulation parameters, Anti-HBs quantitative, HBeAg quantitative, Anti-HBe qualitative.													
Analysis Visit	FU Week 1	FU Week 4		FU Week 12					FU Week 24				FU Week 48/EOFU
Analysis Window	EOT DATE , +7	-14, +28		-28, +42					-42, +84				-84, +14
HBcrAg, HBV RNA.													
Analysis Visit	FU Week 1			FU Week 12					FU Week 24				FU Week 48/EOFU
Analysis Window	EOT DATE , +35			±42					-42, +84				-84, +14
CLDQ-HBV, WPAI:GH.													

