1.2.3. Intervention Groups and Duration

There are 5 cohorts planned in this sub-study.

Table 3: Intervention Groups

Cohort	Study Drug	Dose	Route	Number of Doses	Frequency of Dosing
1a	VIR-3434	300 mg	SC	12	Every 4 weeks
	TDF	300 mg ^b	Oral	\geq 308 ^c	Every day
2a	VIR-3434	Up to 300 mg ^a	SC	12	Every 4 weeks
	TDF	300 mg ^b	Oral	\geq 308 ^c	Every day
3a	VIR-3434	300 mg	SC	4-6 ^d	Every 8-12 weeks ^d
	TDF	300 mg ^b	Oral	\geq 252 ^c	Every day
4a	VIR-3434	300 mg	SC	12	Every 4 weeks
	VIR-2218	200 mg	SC	12	Every 4 weeks
	TDF	300 mg ^b	Oral	\geq 308 ^c	Every day
5a	VIR-3434	300 mg	SC	13	Every 4 weeks
	VIR-2218	200 mg	SC	13	Every 4 weeks
	PEG-IFN α	180 mcg	SC	48	Every week
	TDF	300 mg ^b	Oral	\geq 336 ^c	Every day

^a The dose of VIR-3434 will be determined before participants are enrolled in the cohort.

^b Tenofovir disoproxil fumarate dose (TDF) will be 300 mg as approved by the FDA. Supply outside the United States may be Tenofovir disoproxil (TD) 245 mg.

^c The minimum number of doses received by participant. Participants will continue receiving additional doses of TDF until they qualify for NRTI discontinuation.

^d The dosing regimen will be finalized before participants are enrolled in the cohort.

The total duration in the study for participants will be up to 100 weeks in cohorts 1a, 2a, and Cohort 4a, 92-96 weeks for Cohort 3a, and 104 weeks for Cohort 5a. This includes a Screening Period (up to 56 days or 8 weeks), Treatment Period (44 weeks for cohorts 1a and 2a, 36 or

40 weeks for Cohort 3a, 44 weeks for Cohort 4a, and 48 weeks for Cohort 5a) and a Follow-Up Period (up to 48 weeks) for all cohorts.

Once participants complete the Treatment Period per their respective cohort, they will enter the Follow-Up Period. Participants will discontinue the NRTI at the F1 or F12 visit in the Follow-Up Period if they meet the criteria to discontinue NRTI ([Section 1.2.4](#)) based on the data available. Additional study visits are required for participants who discontinue NRTI in the Follow-Up Period as indicated in the SOA in the study protocol. Participants who discontinue NRTI at F1 visit will be required to return to the site for additional visits at F2, F6, F10, F28, F32, F40, and F44. Participants who discontinue NRTI at F12 visit will be required to return to the site for additional visits at F14, F18, F22, F28, F32, F40, and F44.

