- For efficacy response variables, the missing equals failure (MEF) approach will be used for the analysis, except for the sensitivity analysis for the primary endpoint described in [Section Error! Reference source not found.](#). The sensitivity analysis will be conducted to evaluate the impact of missing data, in which missing data will be imputed.
- Missing data will not be imputed, and will be considered as missing data that will not be included in the data summary statistics and analysis. Qualitative data will be imputed as follows:
 1. HBV DNA, for the analysis of the primary endpoint:

- a. If the missing data is reported as “Target Not Detected (TND)”, then the missing data point will be imputed as 0.
- b. If the missing data is reported as “< LLOQ”, then the missing data point will be imputed 1 unit less than the LLOQ value. That’s the LLOQ for HBV DNA is 20 IU/mL, so 19 IU/mL will be imputed.

2. HBs(e)Ag and Anti-HBs(e), for the analyses of primary and secondary efficacy endpoints:
If the missing data is reported as “Not Detected” or “Nonactive”, then the missing data point will be imputed as 0.
3. HBV RNA, for the analysis of an exploratory endpoint:
 - a. If the missing data is reported as “Not Detected”, then the missing data point will be imputed as 0.
 - b. If the missing data is reported as “< LLOQ”, then the missing data point will be imputed 1 unit less than the LLOQ value. That’s the LLOQ for HBV RNA is 0.49 log U/mL, so 0.48 log U/mL will be imputed.
 - c. If the missing data is reported as “> upper limit of quantification (ULOQ)”, then the missing data point will be imputed as 1 unit greater than the value of ULOQ. E.g., The ULOQ for HBV RNA is 6.0 log U/mL, so 6.1 log U/mL will be imputed.
 - d. If the missing data is reported as “Invalid” or “Quantity Not Sufficient (QNS)”, then the missing data will not be imputed and considered as missing data.
4. HBcrAg, for the analysis of an exploratory endpoint:
 - a. If the missing data is reported as “TND”, then the missing data point will be imputed as 0.
 - b. If the missing data is reported as “Target Detected (TD)”, then the missing data point will be imputed as 1 unit less than the LLOQ. That’s the LLOQ is $3.0 \log_{10} \text{U/mL}$, so $2.9 \log_{10} \text{U/mL}$ will be imputed.

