
9. Proportion of participants achieving sustained suppression of HBV DNA (< LLOQ) with HBsAg loss (< 0.05 IU/mL) after discontinuation of all treatment:
 
a. at 24 weeks
 
b. at the F48 Follow-Up visit
 
11. Proportion of participants achieving sustained suppression of HBV DNA (< LLOQ) after discontinuation of all treatment:
 
a. at 24 weeks
 
b. at the F48 Follow-Up visit
	
Due to early study termination, modification to timepoints of a. and b. as below:
 
a) at 24 weeks after discontinuation of all treatments (an analysis window of 168 ± 14 days will be applied to capture data around the 24 weeks timepoint, following the rules in Appendix 2 for data selection)
 
b) at the last Follow-Up visit, for participants who have > 24 weeks of discontinuation, after discontinuation of all treatments
 
c) at the last Follow-Up visit after discontinuation of all treatments (all participants will be included in the denominator)
 
Specifically, for a) and b), the denominator used in the percentage calculation will exclude participants with uncertain NRTI discontinuation status due to early study termination (e.g., no Follow-Up 12 visit).
 
The number and percentage of participants achieving
 
 • sustained suppression of HBV DNA (< LLOQ) • sustained suppression of HBV DNA (< LLOQ) with HBsAg loss (< 0.05 IU/mL) 
will be summarized by cohort with the two-sided 95% Clopper-Pearson CI.
 
In addition, the number and percentage of participants achieving
 
 • sustained suppression of HBV DNA (< LLOQ), allowing transient viremia

	
 • sustained suppression of HBV DNA (< LLOQ) with HBsAg loss (< 0.05 IU/mL), allowing transient viremia where transient viremia is defined as HBV DNA \geq LLOQ or HBsAg \geq LLOQ for \leq 35 days, adapted from the 2022 American Association for the Study of Liver Diseases (AASLD) – The European Association for the Study of the Liver (EASL) functional cure definition (AASLD-EASL, 2022), will be analyzed similarly. 
Similarly, the analyses above will be repeated after replacing “HBsAg loss (<0.05 IU/mL) with “HBsAg < 100 IU/mL”. Accordingly, the transient viremia is defined as HBV DNA \geq LLOQ or HBsAg \geq 100 IU/mL for \leq 35 days, adapted from the 2022 AASLD-EASL partial functional cure definition (AASLD-EASL, 2022).

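### The 24-week off-treatment window counts from the NRTI stop but follow-up visits count from EOT, so a fully compliant F1 stopper can occasionally have no sample in it and be scored a failure

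*SAP*

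**What the plan says.** All references are to the SAP, which is written for the STRIVE sub-study.

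- **Stopping NRTI (1.2.3):** "Participants will discontinue the NRTI at the F1 or F12 visit in the Follow-Up Period if they meet the criteria to discontinue NRTI".
- **24-week reading (4.4.1, endpoints 9 and 11, timepoint a):** "an analysis window of 168 ± 14 days will be applied to capture data around the 24 weeks timepoint". The days run from discontinuation of all treatments, and samples are picked by the Appendix 2 rules.
- **Window rules (Appendix 2, notes):** "The Analysis Window boundaries are left exclusive, right inclusive, except specified otherwise". Also: "If no numerical measurement is available within an analysis window, the measurement will be considered missing for the visit".
- **Missing responses (4.1):** "For efficacy response variables, the missing equals failure (MEF) approach will be used for the analysis".
- **Denominator (4.4.1):** for timepoints a) and b), "the denominator used in the percentage calculation will exclude participants with uncertain NRTI discontinuation status due to early study termination". A participant known to have stopped at F1 is not in that group and stays in.
- **Visit schedule for F1 stoppers (Appendix 2, Table 12):** F1 at D8 ±2, F24 at D169 ±7 and F28 at D197 ±7, all counted from EOT.

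**The concern.** The window and the visits have different starting points. The window starts when NRTI stops, and the visits start at EOT, about a week earlier for an F1 stopper. F24 is therefore nominally 7 days short of the centre of the window, and F28 is nominally past its upper end. The allowed visit windows can push F24 below the lower limit while F28 stays above the upper one. A participant who is still suppressed, and who attended every visit on an allowed day, would then be counted as not having sustained the response.

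Endpoints 9a and 11a are the off-treatment readings of functional cure and sustained suppression. This mechanism can only lower them. It falls almost entirely on F1 stoppers, who met the NRTI discontinuation criteria at the first opportunity.

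A smaller problem of the same kind sits in Tables 12 and 13. A left-exclusive ±7 analysis window is one day shorter than the ±7 visit window it serves.

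**Working it through.** **Inputs.** Window 168 ± 14 (4.4.1), left-exclusive (Appendix 2). F1 on D6 to D10, F24 on D162 to D176, F28 on D190 to D204 (Table 12). Assumption: the NRTI stop date is the F1 visit date, counted in elapsed days. The SAP gives neither the stop date nor the day-count origin for this window, so both are varied below.

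**The plan's figure.** 24 × 7 = 168. The limits are 168 − 14 = 154 (excluded) and 168 + 14 = 182 (included), so days 155 to 182.

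**Elapsed days after an F1 stop.**
- F24: nominal 169 − 8 = 161; range 162 − 10 = 152 to 176 − 6 = 170.
- F28: nominal 197 − 8 = 189; range 190 − 10 = 180 to 204 − 6 = 198.
- F20 (D141 ±7): at most 148 − 6 = 142, so it never helps.

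**A concrete case.** F1 on D8, F24 on D162 and F28 on D197 are all allowed. The samples fall at 162 − 8 = 154 and 197 − 8 = 189 days. Both are outside.

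**Enumeration of allowed days.**

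| F1 | Window, in follow-up days | F24 days outside | F28 days inside | Combinations with no sample |
|---|---|---|---|---|
| D6 | 161–188 | none | none | 0 |
| D7 | 162–189 | none | none | 0 |
| D8 | 163–190 | D162 | D190 | 1 × 14 = 14 |
| D9 | 164–191 | D162–163 | D190–191 | 2 × 13 = 26 |
| D10 | 165–192 | D162–164 | D190–192 | 3 × 12 = 36 |

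F24 alone misses in 1 + 2 + 3 = 6 of 5 × 15 = 75 day pairs (8.0%). Neither F24 nor F28 is inside in 14 + 26 + 36 = 76 of 5 × 15 × 15 = 1,125 combinations (6.8%).

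**Sensitivity.**
- Stop one day before F1, or stop date counted as Day 1: 14 + 26 = 40 of 1,125 (3.6%).
- Stop one day after F1: 14 + 26 + 36 + 4 × 11 = 120 of 1,125 (10.7%).
- Left boundary made inclusive, stop on the F1 date: 1 × 13 + 2 × 12 = 37 of 1,125 (3.3%).
- Visits clustered around nominal (truncated normal, SD 2 to 4 days): roughly 0.1% to 3.4%.
- F12 stoppers (F12 at D85 ±7, F36 at D253 ±7, F40 at D281 ±7, Table 13): F36 falls at 246 − 92 = 154 to 260 − 78 = 182 days. Only F12 on D92 with F36 on D246 misses, and F40 rescues it on one day of 15. That leaves 14 of 15 × 15 × 15 = 3,375 (0.4%).

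**Effect of one false failure.** 1/10 = 10 points; 1/15 = 6.7 points.

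**Tables 12 and 13.** In Table 12, FU Week 2 (D15, −5/+7) runs through D22, and FU Week 4 (D29 ±7) starts at D23. An F4 visit on D22 is allowed, since 29 − 7 = 22, but it is assigned to FU Week 2, which normally already holds the F2 sample. Appendix 2 rule b) prefers the scheduled measurement and does not say which of two scheduled measurements to take. FU Week 4 is left empty. The same lower edge occurs at FU Weeks 4, 6, 8, 10 and 12 in Table 12 and at FU Weeks 14 to 24 in Table 13.

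**The case against.** The strongest reply is that this is rare and of limited consequence. The nominal F24 sample, at day 161, is inside the window. With the stop on the F1 date, a miss needs F1 on D8 or later together with F24 5 to 7 days early. Nothing in the documents says visits are spread evenly over their windows. Only F1 stoppers who are truly still responding can become false failures; with 5 such participants (an illustration) the expected number is 5 × 0.068 = 0.34 even under even spreading. An unscheduled sample could fill the gap. Timepoint c), the last follow-up visit, does not use the window. The endpoints are secondary in a study without hypothesis testing. All of this stands, and it limits the size of the point. It does not remove it, because the rule as written can turn a compliant responder into a failure.

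A reader might infer more than the documents support:

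- **That the left-exclusive boundary is the cause.** It is only part of it. Including day 154 still leaves 3.3%; the rest is the mismatch between the two starting points.
- **That 6.8% of F1 stoppers will be misclassified, or far more if TDF/TD stops several days after F1.** The percentage counts allowed combinations. Section 1.2.3 places the stop at the visit, and no passage describes a lag of several days.
- **That the Table 12 and 13 edge produces failures generally.** Missing equals failure covers response variables only. HBsAg and HBV DNA levels by visit are simply missing for that week. Only by-visit response proportions (endpoints 15 and 16, and the HBeAg proportions) could be scored as failures, and the primary endpoint is read at EOT.
- **That the point applies to THRIVE.** The protocol supplied is for THRIVE, where TDF ends with the last dose of the other study drugs (Protocol 4.3.3), so there is no F1 stop. The point rests on the STRIVE SAP alone.

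**Conclusion.** The point holds as an edge case. Under the SAP's own rules, an F1 stopper with every visit inside its allowed window can have no scheduled sample in days 155 to 182 and be counted as a failure for endpoints 9a and 11a. With the stop on the F1 date, 6.8% of allowed day combinations do this. A one-day shift in the stop date moves the figure between 3.6% and 10.7%, and clustered visit timing brings it down to roughly 0.1% to 3.4%. F12 stoppers are almost untouched.

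The expected number of affected participants is small. The point is still worth correcting because the bias has one direction, the cohorts are small and the result would depend on visit timing that nobody got wrong. The undefined stop date is part of the same problem, since the figure moves with it. The Table 12 and 13 edge is secondary: a real gap in the rules, which matters only for a visit exactly 7 days early.

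**What to change.** **Timepoint a), endpoints 9 and 11.** Use the scheduled F24 visit for F1 stoppers and the scheduled F36 visit for F12 stoppers. Alternatively, widen the window only as far as needed, for example 168 −16/+14 days with both ends included (days 152 to 182). With the stop on the F1 date or the day before, that leaves 0 of 1,125 combinations empty for F1 stoppers. With the stop on the F12 date, it leaves 0 of 3,375 for F12 stoppers. If the stop is one day after F1, F24 can fall at day 151 and 11 of 1,125 (1.0%) remain, so the visit-based rule is the more robust of the two.

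**Stop date.** State the date from which the days are counted (the last TDF/TD dose) and whether that date is Day 0 or Day 1.

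**Appendix 2.** Assign a scheduled visit made within its protocol visit window to its own nominal analysis visit. Keep the day windows for unscheduled or out-of-window samples.

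**Cost.** A few sentences of SAP text and minor reprogramming. Some F1 stoppers' 24-week readings will be taken at about 22 to 23 weeks after the stop (152/7 = 21.7 at the earliest, 161/7 = 23 nominally). A much wider window, such as 168 ± 21 days, is not needed. It would start at day 147, and since F32 falls 126 to 154 days after an F12 stop, it would let an F32 sample stand in for a missed F36.
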